Official Title: Interactive Book Reading to Accelerate Word Learning by Children with SLI

Grant #: R01DC012824

NCT#: NCT01829360

Date: October 18, 2019

Purpose. The goal was to determine whether interactive book reading outcomes for children with SLI were affected by manipulation of dose (i.e., the number of exposures to the target word during a book reading session) and dose frequency (i.e., the number of repeated book reading sessions) and whether pre-treatment factors predicted treatment response variation.

Participant Selection. Kindergarten children are recruited through community language screenings, referrals from speech-language pathologists, or advertisements. At first contact with an interested family, an informed consent document and background questionnaire are provided. The background questionnaire gains information about demographic characteristics of the child/family and assesses some of the inclusionary/exclusionary criteria.

Exclusionary Criteria: a child is excluded from participation if he/she:

- (1) speaks more than one language, as determined by background questionnaire;
- (2) has a health history indicating neurologic or other disorders that would exclude a diagnosis of SLI (e.g., autism), as determined by background questionnaire.

[figure not shown]
Inclusionary Criteria: children will

- (1) be at least 5-years-old and in/eligible for kindergarten, as determined by background questionnaire;
- (2) pass a hearing screening;
- (3) have nonverbal IQs at or above the 16th percentile on the *Reynolds Intellectual Assessment Scale-2* to rule out cognitive deficits;
- (4) have a Core Language Score at or below the 9th percentile (standard score = 80, 1.3 SD below mean) on the *CELF-4* to document language impairment;
- (5) score at or below the 9th percentile (standard score = 6) on the semantics subtest of the *DELV* or the word classes subtest of the *CELF-5* to document a vocabulary deficit. Score cut-offs are based on classification accuracy reported in the manuals (when reported).

[figure not shown]
Procedural flowchart. Is shown in the following multi-page figure. Each major procedure is described below.

[figure not shown]
Standardized Testing: Once informed consent is attained, standardized tests are administered to assess inclusionary criteria and gain additional information to further characterize the participants and potentially predict their performance in treatment.

[figure not shown]
- Pre-Session 1
 - Signed consent form (could be completed at Session 1)
 - Completed background questionnaire (could be completed at Session 1)
- Session 1
 - CELF-4: Core Language Subtests (inclusionary criteria)
 - CTOPP-2: Phonological Awareness – Elision subtest (further characterize participants)
- Session 2
 - DELV Semantic subtest (inclusionary criteria)
 - CELF-4: Word Classes subtest (inclusionary criteria)
 - CTOPP-2: Phonological Awareness – Sound Matching subtest (further characterize participants)
- Session 3
 - Hearing screening (inclusionary criteria)
 - RIAS (inclusionary criteria)
 - CTOPP-2: Phonological Awareness – Blending subtest (further characterize participants)
 - CTOPP-2: Phonological Memory subtests (further characterize participants)
 - GFTA-2: Articulation (further characterize participants)

[figure not shown]

O

Randomization. Once children have met all criteria to be included in the study, they are randomized to one of the 4 treatment arms, shown in the next figure. Treatment arm randomization also includes assignment of Set A and Set B books to each treatment. Stratified randomization was used such that children with DELV standard scores 6 and higher are randomized separately from children with DELV scores 5 and lower because it was hypothesized that treatment outcomes would differ based on the ability to quickly learn new words, as indexed by the DELV.

Treatment. See https://asha.figshare.com/articles/Dose_Dose_Frequency_Storkel_et_al_2019_9745181
Supplemental Material S4. Treatment scripts for each treatment condition and each word set for the treatment protocol (session-by-session list of activities and treatment scripts) corresponding to each arm and word set.

[figure not shown]
Outcome Measures.

Primary outcome measure: Definition task. As in our prior preliminary clinical trial (Storkel, Voelmle, et al., 2017), the primary outcome measure was a definition task. We chose a definition task for two reasons: (1) to afford comparison to our past research with this treatment to determine whether continuing changes to the treatment improve outcomes; (2) to ensure that the treatment is helping children establish the rich word knowledge needed to support a variety of linguistic tasks. Although this task sets a high bar for word learning, our past research shows that it is sensitive enough to detect changes between different treatment conditions. The definition task was administered before treatment, immediately following the conclusion of each treatment, and 2 weeks following the conclusion of each treatment

Research assistants administer the task across two sessions with 15 Set A and 15 Set B words tested in each session. For each word, the child received the prompt, “Tell me what [word] means.” Prompts were pre-recorded and presented with computer software so that pronunciations of the words were consistent across tasks. Children’s responses were audio recorded and transcribed for later scoring. The children first hear three practice words (*bed, ball, candy*), which were words likely to be known by them to ensure that they understood the task. Then, the 30 target words are presented in random order along with familiar words ($n = 10$, e.g., *chair, teacher, apple*). In terms of training the testers, all testers are shown how to use the computer software and the recording device. Testers practice administering the definition test to other trained testers until they are comfortable with the equipment and protocol. Testing script is available at https://asha.figshare.com/articles/Dose_Dose_Frequency_Storkel_et_al_2019_9745181 *Supplemental Material S7 Testing script.*

The definition scoring procedures from our prior preliminary clinical trial (Storkel, Voelmle, et al., 2017) are used. In the prior study, the research team followed the procedures of McGregor, Oleson, Bahnsen, and Duff (2013) and consulted dictionaries to create a scoring rubric that listed common elements of an accurate and complete definition for each word (e.g., pouted = negative emotion + lips/face). Possible scores were: 0 points for an incorrect or absent definition (e.g., pouted = face), 1 point for an appropriate use of the word in a sentence (e.g., pouted = pouted because you don’t want to eat and your mom makes you) or for a vague definition (e.g., pouted = cry), 2 points for a conventional definition containing at least one critical element but lacking other critical elements (e.g., pouted = mad), and 3 points for a complete and accurate definition including all critical elements (e.g., pouted = feel mad and push your lips out). Two raters independently score each response following the rubric guidelines. The raters compare their scores and resolve disagreements through consensus.

In the analyses, children’s definitions scored as 2 or 3 (i.e., a partially or completely accurate definition) are counted as correct and definitions scored as 0 or 1 (i.e., incorrect definition, absent definition, correct use of a word in a sentence, or vague definition) are counted as incorrect. This was done to afford comparison to prior studies (Justice et al., 2005; Storkel, Voelmle, et al., 2017).

Secondary outcome measure: Interim definition. Learning also is tracked during treatment. The research assistant who provides the treatment prompts children to provide definitions or name the target words at four points during each treatment. The words are assessed in a fixed order while the child views the pre-reading pictures for each word. The research assistant asks, "What does [word] mean?". Specific feedback is not provided but the correct definition always is provided after the child's response regardless of the accuracy of the response. This is shown in the scripts at

https://asha.figshare.com/articles/Dose_Dose_Frequency_Storkel_et_al_2019_9745181. Definition responses were scored by two independent raters unaware of children's treatment assignment following the procedures described above.

Secondary outcome measure: Interim naming. For naming prompts, the research assistant shows the child the post-book reading picture without the orthographic label and asks a question meant to elicit the phonological form of the target word (e.g., "What is the lightning doing?" to elicit flashing). Specific feedback is not provided but the correct orthographic label and context sentence always are provided after the child's response regardless of the accuracy of the response. This is shown in the scripts

https://asha.figshare.com/articles/Dose_Dose_Frequency_Storkel_et_al_2019_9745181. Naming responses were scored as correct or incorrect. Correct responses included the word itself (e.g., glared), the word in its bare form or with a different ending (e.g., glare, glaring) or an acceptable phonological substitution of the word (e.g., gwareing, judged on an individual basis). One independent judge scored naming responses and scores were verified by another judge.

Summary of the Design. The preceding figure provides a summary of the design. Upon meeting the selection criteria, children were randomized to 1 of 4 treatment arms. Pre-treatment definition testing was conducted for all 60 words, as indicated by the white box in Figure 1. Treatment 1 then was initiated for 30 words (Set 1 words with Set A or B being randomized to Set 1 or Set 2). Set 1 words were tested via naming and definition tasks four times during Treatment 1, as indicated by asterisks in the figure. Upon completion of Treatment 1, all 60 words (Set 1 and Set 2) were tested immediately and 2-weeks after treatment via the definition task. Note that Set 1 words have received treatment but Set 2 words have not yet received treatment and serve as untreated control words. Treatment 2 was then initiated for the remaining 30 word (Set 2 words). Set 2 words were tested via naming and definition tasks four time during Treatment 2, as indicated by the asterisks in the preceding figure. Upon completion of Treatment 2, all 60 words (Set 1 and Set 2) were tested immediately and 2-weeks after treatment via the definition task. Note that Set 2 words have just received treatment, whereas Set 1 words received treatment much earlier. Thus, for Set 1 words, these test points indicate longitudinal maintenance of learning following 5-12 weeks of treatment on a different word set.

Data Analysis Strategy. A series of multilevel longitudinal models were evaluated using SAS Proc Mixed to describe the change in number of Set 1 and Set 2 words accurately defined over seven test points: pre-treatment, 36 exposures in Treatment 1 (i.e., last Treatment 1 session), immediate post-Treatment 1, 2-week post-Treatment 1, 36 exposures in the second treatment (i.e., last Treatment 2 session), immediate post-Treatment 2, and 2-week post-Treatment 2. Because the number of exposures varied for the interim definition tests, only the 36-exposure interim definition test data, which was consistent for all treatment conditions, were used. We expected significant slopes for Set 1 words during Treatment 1 when they were the target of intervention. We had no hypotheses about whether Set 1 words would decline or would be maintained after Treatment 1 ended and monitoring continued during Treatment 2. We expected non-significant slopes for Set 2 words during Treatment 1, when those words were not the focus of intervention, and significant slopes for Set 2 words during Treatment 2 when they were the target of intervention. Because the number of words defined were counts, the natural log of the words defined was modeled resulting in a model equivalent to a generalized linear mixed model with a negative binomial link function.

The significance of fixed effects was evaluated using Wald tests, and the significance of random effects was evaluated using likelihood ratio tests and information criteria between models with the same fixed effects. We evaluated models with time coded as days since the start of intervention as well as categorically by intervention point. The categorical model fit the data better. The final categorical coding of time is shown in Table 7. Because there were two treatment phases (Treatment 1 vs. Treatment 2) with different expectations for change in Set 1 versus Set 2 words in each phase, we examined a piecewise model of change in which the change related to the first treatment phase (i.e., pre-treatment, 36 exposures in Treatment 1, immediate post-

Treatment 1) was described by one linear slope and change related to the second treatment phase (i.e., 2-week post-Treatment 1, 36 exposures in the second treatment, and immediate post-Treatment 2) was described by a second linear slope. This allows the slope for each word set to differ across each phase, as predicted.

Results. Results are reported fully in Storkel, H. L., Komesidou, R., Pezold, M. J., Pitt, A. R., Fleming, K. J., & Romine, R. S. (2019). The impact of dose and dose frequency on word learning by kindergarten children with developmental language disorder during interactive book reading. *Language, Speech, and Hearing Services in Schools*, 50, 518–539. https://doi.org/10.1044/2019_LSHSS-VOIA-18-0131 - open access

Summary of Results. Results showed that children with DLD learned a significant number of words during treatment regardless of the dose and dose frequency format, but that significant forgetting of newly learned words occurred in all formats once treatment was withdrawn. Individual differences in word learning were related to CELF Core Language and CELF Understanding Spoken Paragraphs scores.

Conclusion. When administered at an adequate intensity, variation in the dose and dose frequency of interactive book reading does not appear to influence word learning by children with DLD. Although interactive book reading continues to show promise as an effective word learning intervention for children with DLD, further development is needed to enhance the effectiveness of this treatment approach.

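### Randomisation is stratified by DELV, but the described model does not name the stratum; adding it with its slope interactions is a cheap, minor improvement to a between-child dose comparison

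*Combined protocol and SAP*

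**What the plan says.** **Allocation.** Under Randomization, eligible children enter at random: "they are randomized to one of the 4 treatment arms, shown in the next figure". Allocation is stratified, so that "children with DELV standard scores 6 and higher are randomized separately from children with DELV scores 5 and lower". The reason given is prognostic: "it was hypothesized that treatment outcomes would differ based on the ability to quickly learn new words, as indexed by the DELV". No block size, allocation ratio or other restriction within strata is described.

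**Eligibility.** Under Inclusionary Criteria, the vocabulary criterion is to "score at or below the 9th percentile (standard score = 6) on the semantics subtest of the" DELV, or alternatively on a CELF word classes subtest. A child can therefore qualify through the CELF with a DELV score above the cut-off, and the upper stratum has no ceiling.

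**Analysis.** Data Analysis Strategy states that "A series of multilevel longitudinal models were evaluated using SAS Proc Mixed". The outcome is the log of the number of words defined. The model is built from word set, test point and a linear slope for each treatment phase: "This allows the slope for each word set to differ across each phase, as predicted". Fixed effects are judged by Wald tests. The text writes out no DELV, arm, dose or dose-frequency term.

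**Aims and results.** Purpose includes asking "whether pre-treatment factors predicted treatment response variation", so predictor models of some kind were intended. Summary of Results names two CELF scores as related to learning and does not mention DELV. The Conclusion on dose and dose frequency is null.

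**The concern.** The design treats DELV as prognostic, and the analysis as described does not use it. When a factor related to outcome is left out of the model, its variance stays in the error term of any between-child comparison. Estimates remain unbiased, but the interval for a dose contrast is wider than it need be. If the stratification also balanced the arms on that factor, the model-based standard error overstates the true sampling variation, and the test rejects less often than its nominal level.

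This matters a little more than usual here because the dose conclusion is null. A statement that dose and dose frequency made no apparent difference is only as informative as the interval behind it, and that interval should respect the groups within which children were randomised.

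**Working it through.** **Inputs.** The document states no sample size, variance, effect size, alpha or power, so there is no figure of the plan's own to reproduce. Every input below is assumed: two-sided alpha of 5%, and a share R² of the dose contrast's variance explained by DELV stratum of 0-20%. The contrast is taken as between children, since children are randomised to arms.

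**Step 1: standard error and power.**

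- SE ratio, unadjusted to adjusted: k = 1/√(1 − R²).
- Arms balanced within strata: the true sampling SD is the adjusted one, but the test uses the larger SE. Type I error = 2(1 − Φ(1.96k)). For a contrast with 80% power when adjusted, unadjusted power = Φ(2.80 − 1.96k).
- Allocation unrestricted within strata: the unadjusted SE is correct for its own sampling variation. Type I error stays at about 5%, and power = Φ(2.80/k − 1.96).

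| R² | SE larger by | Type I, balanced | Power, balanced | Power, unrestricted |
|---|---|---|---|---|
| 0% | 0% | 5.0% | 80% | 80% |
| 2% | 1% | 4.8% | 79% | 79% |
| 10% | 5% | 3.9% | 77% | 76% |
| 20% | 12% | 2.8% | 73% | 71% |

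For R² = 20%: k = 1/√0.80 = 1.118; 1.96 × 1.118 = 2.19, giving 2.8%; Φ(2.80 − 2.19) = 73%; Φ(2.80/1.118 − 1.96) = 71%.

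**Step 2: what gap between strata this implies.** For strata in proportions p and 1 − p whose mean slopes differ by d within-stratum SDs, R² = p(1 − p)d²/(1 + p(1 − p)d²). With equal strata, d = 0.5 gives 0.0625/1.0625 = 6% and d = 1 gives 0.25/1.25 = 20%. The 20% is not a ceiling: d = 1.5 gives 0.5625/1.5625 = 36%, and an SE 25% larger. Unequal strata reduce it: 30:70 with d = 1 gives 0.21/1.21 = 17%, and an SE 10% larger.

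**Step 3: balance within strata decides whether the SE is wrong or only inefficient.** In a child-level simulation (one slope per child, four arms, 40 children, equal strata, 1 SD gap, 3-df test), unadjusted type I error was 2.3% with arms balanced within strata and 5.1% with simple randomisation. A second check gave 1.8% and 5.6%. Under simple randomisation, adjustment still narrowed the interval by 9%.

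**Step 4: the term needed is an interaction.** The described model tests slopes. In a random-intercept-and-slope simulation (40 children, three time points), the mean SE of the dose-by-time term was:

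| DELV affects | No stratum | Stratum main effect | Stratum and stratum-by-time |
|---|---|---|---|
| slope | 0.1656 | 0.1656 | 0.1427 |
| level only | 0.1376 | 0.1376 | 0.1375 |

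A main effect alone gains nothing, and nothing is gained if DELV shifts only the level.

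**Step 5: closer to the described model.** In a piecewise mixed-model simulation with two word sets, two phases, 40 children and balanced arms, a 1 SD gap in child slope gave SEs of 0.5560 without and 0.5027 with the stratum terms (10.6% larger). When child-slope variance made up 48% rather than 79% of the contrast's variance, the figures were 0.6919 and 0.6469 (7.0%). For a within-child comparison of formats, both SEs were 0.0747, so there was no gain.

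**Step 6: cost if DELV has no effect.** In a child-level model with one added stratum term, the interval widens by the ratio of t quantiles on N − 5 and N − 4 df when arms are balanced: 0.1% at N = 40 and 0.3% at N = 24. With unrestricted allocation, a further factor of √(1 + 1/(N − 6)) for chance imbalance brings this to about 1.5% and 3%.

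**The case against.** The strongest reply is that no omission is shown. Data Analysis Strategy is a summary that writes out no arm, dose or covariate term, so its silence on DELV is weak evidence. It refers to a table that is not in the text, and full results are left to a publication. This stands, and is why the point is conditional. A reader might infer that the dose analysis ignored the stratification; the document does not establish that.

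A reader might also infer that the reported standard errors are overstated and the tests conservative. That needs arms balanced within strata. Separate randomisation is stated, but blocking or any other restriction is not. Without it, the unadjusted analysis is valid and merely less precise.

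The contrast may not be wholly between children. Each child receives two treatments and the arms figure is not shown. If format differs between a child's two treatments, a general DELV effect cancels from that within-child comparison.

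The size is speculative. The open-ended upper stratum makes a gap between strata possible, but the results summary lists only CELF scores as related to learning, which is compatible with a small DELV effect. These objections limit the point. They do not remove the case for saying how the stratification factor was handled.

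**Conclusion.** A minor point, and a cheap improvement. The design stratifies on a factor it calls prognostic, and the analysis as written does not mention it. If the stratum was left out of the dose model and the strata differ in learning slope, the standard error of a between-child dose contrast is about 0-12% larger than necessary for an assumed R² of 0-20%. At the top of that range, a contrast with 80% power when adjusted would have 73% (balanced arms) or 71% (unrestricted allocation) without the stratum. Larger gaps would give more; a level-only effect or a within-child contrast would give none.

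There is no bias in the dose estimate. A reader might go further and infer that the null dose result was produced by leaving DELV out, or that a real dose effect was missed. The document gives nothing from which that could be shown: no sample size, variance, estimate or interval, and no evidence that DELV was related to learning. Nor is adjustment entirely free, since it costs a little precision if DELV has no effect.

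**What to change.** State whether DELV stratum was in the model that tested dose and, if it was, in what form. State also whether allocation was blocked or otherwise restricted within strata.

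If the stratum was not in the model, refit it with DELV stratum and its interaction with each treated-word slope that is tested: Set 1 in the first phase and Set 2 in the second. Report the dose contrasts and their intervals beside the null conclusion, as a sensitivity analysis labelled post hoc. The covariate was fixed by the randomisation rather than chosen from the data, but the dose result is already known, so the label is needed.

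The cost is a few fixed-effect parameters and one re-run, with no new data. If DELV turns out not to matter, the loss of precision is the small widening worked out above. That figure is for one stratum term in a child-level model; separate interactions for each slope, or dropout, could cost slightly more.

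### Book set (A or B) is randomised for each child, but the described model names no A/B term; a difference between the sets would cost precision and allow chance imbalance, without bias

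*Combined protocol and SAP*

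**What the plan says.** The Randomization section makes book set part of the allocation: "Treatment arm randomization also includes assignment of Set A and Set B books to each treatment". The Summary of the Design repeats this for the words: "Set 1 words with Set A or B being randomized to Set 1 or Set 2". Each set has 30 words, and both are measured at the start: "Pre-treatment definition testing was conducted for all 60 words".

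The within-child control during Treatment 1 is the other set: "Set 2 words have not yet received treatment and serve as untreated control words". Treatment 2 then targets that set, so every child is eventually treated on both A and B.

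The only stratifier named is the DELV score: "children with DELV standard scores 6 and higher are randomized separately from children with DELV scores 5 and lower". No blocking or balancing of A/B within the four arms is described, and the document does not say that the sets were matched for difficulty.

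The Data Analysis Strategy sets out mixed models "to describe the change in number of Set 1 and Set 2 words accurately defined over seven test points", with separate linear slopes for the two treatment phases. The word-set factor there is order of treatment. Book set is not mentioned.

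**The concern.** Set 1 and Set 2 are labels for treatment order. The physical words behind them differ from child to child: in some children the treated set is A and the control is B, in others the reverse. If the A words are learned more readily than the B words, one group's treated-minus-control difference is pushed up and the other's is pushed down. A model that does not know which child is which treats this known difference as unexplained variation between children.

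There are two consequences. The first is lost precision in both the treated-versus-control and the between-arm comparisons. The second is that, if A/B was not balanced within arm, a small arm may by chance have mostly one set treated first, and this could mimic or mask a format effect. Both matter most for the reported conclusion that varying dose and dose frequency does not appear to influence word learning, because avoidable noise favours a null finding.

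**Working it through.** **Nothing to reproduce.** The document gives no sample size, power, SD or effect size. All sizes below rest on assumed values and are illustrative.

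**Inputs from the document.** A/B is randomised per child (Randomization; Summary of the Design); there are four arms; all 60 words are tested before treatment; the analysis is of slopes.

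**Assumed inputs.** 1:1 allocation of A/B; an A-B difference in gain, D, of 0 to 3 words; an SD of the within-child treated-minus-control difference, σ, of 3 words; 5 to 20 children per arm; two-sided α of 0.05. The arithmetic is on the raw word scale, although the plan models the natural log of the count.

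**Step 1: shift per child.** Let s be the amount by which book set moves a child's treated-minus-control difference, +s or −s with probability 1/2 each. If the sets differ only when taught, s = D/2. If they differ by the same amount when untaught, s = D. The plan expects no significant slope for untreated words, so s = D/2 is the main case.

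**Step 2: bias.** The expected shift is ½(+s) + ½(−s) = 0, in the treated-versus-control contrast and in any between-arm difference.

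**Step 3: precision.** The standard error is inflated by √(1 + s²/σ²).

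| D (words) | s = D/2 | s = D |
|---|---|---|
| 1 | √(1 + 0.25/9) = 1.014 | √(1 + 1/9) = 1.054 |
| 2 | √(1 + 1/9) = 1.054 | √(1 + 4/9) = 1.202 |
| 3 | √(1 + 2.25/9) = 1.118 | √(1 + 9/9) = 1.414 |

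The main case gives about 1%, 5% and 12%.

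**Step 4: chance imbalance in a single-phase contrast.** The chance SD of a between-arm difference is s√(2/n). With s = D/2 this is D√(0.5/n): 0.32D at n = 5 per arm and 0.16D at n = 20. With s = D it is 0.63D and 0.32D. As an example, take an arm of 8 under simple allocation. The probability of a 6:2 or more extreme split is 2(28 + 8 + 1)/256 = 0.289. With s = D/2, a 6:2 split moves that arm's mean by D(0.75 − 0.50) = 0.25D, or 0.25 to 0.75 words for D of 1 to 3.

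**Step 5: simulation.** There were 6,000 runs per scenario, with 6, 10 or 16 children per arm, s from 0 to 3 and a linear simplification of the mixed model.

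- With no true effect, the mean estimate stayed within about 0.02 words of zero.
- Under simple allocation without an A/B term, type I error was nominal: 0.047-0.056 for treated versus control and 0.046-0.056 between arms.
- Under balanced allocation without the term, the tests were conservative: about 0.04 at s = 1, 0.02 at s = 2 and 0.005 at s = 3.
- At 6 per arm, simple allocation and an assumed true treated-versus-control effect of 1.8 words, adding the term changed power from 0.76 to 0.79 (s = 1), 0.65 to 0.78 (s = 2) and 0.51 to 0.79 (s = 3). At s = 0 it fell slightly, from 0.81 to 0.78.

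In the main case, D = 2 corresponds to s = 1, so the larger gains need a large D or sets that also differ when untaught.

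**The case against.** The strongest objection is that randomisation has already dealt with this. A reader might infer that an A-B difference contaminates every treated-versus-control and between-arm contrast. The document does not support that. Allocation of A/B is random, so the difference has expectation zero, and leaving out a randomised factor keeps the tests valid. This part of the objection stands in full.

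Three further points stand in part.

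- **Silence about the model.** A reader might also infer that the model certainly contained no A/B term. The Data Analysis Strategy does not list all fixed effects; it names no arm, dose or CELF term either, yet results are reported for these. The design figure is not shown. What can be said is that no A/B term is named.
- **Two phases.** Every child is treated once on A and once on B. If an arm keeps one format in both phases, which the visible text does not state, an additive difference cancels when treated learning is pooled over phases: D/2 − D/2 = 0. The imbalance in Step 4 then applies to single-phase contrasts only.
- **Baseline testing.** A constant difference in how many words can already be defined largely drops out of slopes. A difference in learnability does not. Nor is the removal exact on the log scale: with assumed counts, a 3-word gain from 1 word is ln(4/1) = 1.39, and from 2 words it is ln(5/2) = 0.92.

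Finally, nothing in the document shows that the sets do differ, and set assignment may have been blocked along with arm. Blocking would remove the chance imbalance, but an unadjusted test would still be conservative if the sets differ.

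**Conclusion.** A limited point about precision and chance imbalance holds. A/B is a randomised factor that should be known for every child, the described analysis does not name it, and its balance within arm is not stated. The likely cost is modest: about 1% to 12% on the standard error for an A-B difference in gain of 1 to 3 words, given an assumed SD of 3 words and sets that differ only when taught. It is larger if they also differ untaught, and zero if there is no difference. The document does not show that any reported result is biased or that the dose conclusion is wrong. It leaves open how much avoidable noise, or a chance A/B imbalance in small arms, contributed to that null finding.

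**What to change.** In the model of the Data Analysis Strategy, add the assigned book set (A versus B) and its interaction with the treated-phase slope as fixed effects. Coding the set as ±½ keeps the main slopes as averages over the two sets. Base the treated-versus-control and arm comparisons on this model. Report the number of children with A and with B treated first in each arm, and say whether that assignment was blocked. If the reported model already contained these terms, stating so and giving the split is enough.

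Because results have been reported, this means a refit of existing data. The allocation should already be on file, and the definition task identifies Set A and Set B words, so no new data are needed. The cost is a few degrees of freedom and, if the sets do not differ, a slight loss of power (0.81 to 0.78 in the smallest scenario simulated). Interactions of book set with arm would cost more and are not needed for this purpose.
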